Evaluation of changes of core symptoms and their clinical significance: In each therapeutic condition the improvement of each patient in measures of the primary and secondary outcome criteria will be estimated by the Reliable Change Index (RCI) (Wise, 2004)(Jacobson and Truax, 1991), which summarizes changes at the level of an individual in the context of observed changes for the whole sample. The RCI provides information about the functioning of an individual before/after therapy on an outcome measure, including the normative information about this measure (Atkins *et al.*, 2005) by dividing the difference between pre- and post-treatment scores by the standard error (that includes also the reliability coefficient, not only the standard deviation of the measure) (Hurst and Bolton, 2004). The change will be considered as being unlikely the product of measurement error (i.e., considered reliable), if the RCI is greater than 1.96. When the individual has a change score greater than 1.96 it can be assumed that the individual has improved.

Follow-up (T0-T1, T1-T2, T0-T2) analysis of treatment effects on MRI target parameters (RSFC, Glx, GABA) and of potential associations between these neurobiological changes and clinical improvement according to outcome criteria

Separate for rs-fMRI and ¹H-MRS data: Analysis of variance (ANOVA) for repeated measures will be applied to test for effects of group belonging (ST-EF, ST-AC, and healthy subjects; ST-EF vs. ST-AC) on changes of RSFC, Glx and GABA over time, as well as for within-subject changes between T1 and T2 scans.

Associations between RSFC and the local Glx and GABA concentrations: A linear mixed model analysis will be performed to investigate changes after 9 weeks (and 6 month respectively) of either therapeutic condition (ST-EF, ST-AC) compared to unspecific changes over time in healthy controls as well as between treatment groups. In a first step, this analysis will be performed separately in both treatment groups and healthy controls and for both neurotransmitters (Glx, GABA) and both spectroscopic and functional connectivity target regions (aMCC, DLPFC). In the second step, potential treatment condition driven differences in the correlations between metabolic and RSFC parameters will be investigated by applying the same model including the factor treatment group.

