Interrelation between clinical outcome parameters and neurobiological findings: A linear mixed model analysis will be used that includes those MRI-data (RSFC, Glx, GABA) that have been significantly affected by therapy (**T0-T1**, **T1-T2**, **T0-T2**) and those clinical scores that reached the highest RCI. The detected significant interactions will be compared between the ST-EF and ST-AC treatment condition.

Data handling

Prior to starting recruitment of the participants, a project specific database will be created, which considers all GCP requirements in terms of user authentication, anonymization of participants, audit log and query management. This database will contain all project related data (demographic data, RSFC, ¹H-MRS and psychopathology data). All clinical ratings will be determined according to the corresponding manuals and will be separately stored for the time points T0, T1 and T2.

MRI data (anatomic and rs-fMRI data) will be acquired in the DICOM-Standard format, ¹H-MRS data are collected in a vendor specific format (.rda and .dat Siemens files). All raw and processed data are stored on a RAID computer system, which is serviced by the MPJ and equipped for standardized data access and management. All data will be available to longitudinal research and joint research with cooperation partners in this field.

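### Repeated-measures ANOVA of MRI change drops participants with a missing scan; a mixed model on all scans, informed by clinical predictors of scan loss, is a cheap improvement valid only under missing-at-random

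*SAP*

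**What the plan says.** The relevant SAP section is headed "Follow-up (T0-T1, T1-T2, T0-T2) analysis of treatment effects on MRI target parameters (RSFC, Glx, GABA", so it names three intervals. Its paragraph on separate rs-fMRI and ¹H-MRS analyses reads "Analysis of variance (ANOVA) for repeated measures will be applied to test for effects of group belonging". The groups and measures are given as "ST-EF, ST-AC, and healthy subjects; ST-EF vs. ST-AC) on changes of RSFC, Glx and GABA over time", and the sentence ends "as well as for within-subject changes between T1 and T2 scans". SPSS is named at the start of the SAP.

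Linear mixed models are planned elsewhere. The paragraph on associations between RSFC and the metabolites says "A linear mixed model analysis will be performed to investigate changes after 9 weeks (and 6 month respectively) of either therapeutic condition". The paragraph on the interrelation with clinical outcome says "A linear mixed model analysis will be used that includes those MRI-data (RSFC, Glx, GABA) that have been significantly affected by therapy", again for the three intervals. Under Data handling, clinical ratings are to be "separately stored for the time points T0, T1 and T2".

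The supplied text does not say how a missed or unusable scan is treated, or whether the group test is one three-visit fit or a set of two-visit fits. It gives no sample size, expected scan loss or correlation between visits.

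**The concern.** A participant scanned at T0 and T1 but not at T2 contributes nothing to the ANOVA of T0-T2 or T1-T2. In a joint three-visit fit, that participant is lost from T0-T1 as well. Two things follow. Precision is lost, because the earlier scans carry information about the missing one. And if the people who lose their T2 scan differ on an earlier MRI value, the completers give a biased picture of change. For the within-subject T1-T2 test this happens even when loss works identically in every group, because there is no comparison group to cancel it.

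The results feed forward: only MRI measures that therapy has significantly affected enter the model relating MRI to clinical outcome. Which scans enter the change tests can therefore influence which measures are carried into that model.

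**Working it through.** The plan has no figure of its own to reproduce. All inputs below are assumptions: unit SD at each visit, T2 loss q of 20-40%, correlations of 0.3-0.9, and logistic loss with a slope of 1 per SD of the variable driving it. That slope is one chosen strength.

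**Precision, only T2 missing at random, equal correlation ρ, T0 means free.** With n participants in a group:
- Complete-case variance of T0-T2: 2(1−ρ)/[n(1−q)].
- Mixed-model variance: [(1−ρ)/(1+ρ)] × [(1+2ρ)/(1−q) + 1]/n.
- SE ratio, complete case to mixed model: √{2(1+ρ)/[2(1+ρ) − q]}.

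Example, ρ = 0.5 and q = 0.3: √(3/2.7) = 1.054. By symmetry T1-T2 is the same, and it does not matter whether the ANOVA is joint or pairwise.

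| ρ | q = 20% | q = 30% | q = 40% |
|---|---|---|---|
| 0.3 | 1.041 | 1.063 | 1.087 |
| 0.5 | 1.035 | 1.054 | 1.074 |
| 0.7 | 1.031 | 1.047 | 1.065 |
| 0.9 | 1.027 | 1.042 | 1.057 |

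For T0-T1 the ratio is 1/√(1−q) = 1.118, 1.195, 1.291 in a joint fit, and 1.000 in a pairwise fit.

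**Within-subject T1-T2, loss depending on T1, no true change.** Mean T1 among those with a T2 scan is −0.173, −0.253 and −0.332 SD at 20, 30 and 40% loss. Their expected T2 is corr(T1,T2) times that, so the bias in change is (1 − corr) × 0.173, 0.253 or 0.332. At 30% loss:
- corr 0.3: 0.7 × 0.253 = 0.177
- corr 0.5: 0.126
- corr 0.7: 0.076
- corr 0.9: 0.025

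With 30 completers, a paired t test at nominal 5% then rejects in 12.8%, 10.5%, 8.2% and 6.0% of trials (noncentral t).

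**Arm contrast, 30% T2 loss selective in one arm.** Simulation, 2,000,000 participants, correlations T0T1 0.6, T0T2 0.5, T1T2 0.6. Bias in SD; the T0-T1 column applies only to a joint fit.

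| Loss depends on | T0-T1 | T1-T2 | T0-T2 | Mixed model, T0-T2 |
|---|---|---|---|---|
| T1 | −0.10 | +0.10 | 0.00 | 0.00 |
| T0-T1 change | −0.21 | +0.08 | −0.13 | 0.00 |
| unseen T2 | −0.03 | −0.10 | −0.13 | −0.16 |

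The 0.00 for T0-T2 under T1-driven loss arises because corr(T0,T1) equals corr(T1,T2). Other correlations gave about 0.05 in either direction. The mixed model is unbiased in the first two rows because there loss depends only on values it contains.

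**Loss driven by a clinical score.** About 25% T2 loss in each arm, score-driven in one arm only; score correlated 0.4 with T1 and T2 MRI and 0.2 with T0 MRI. Bias in the T0-T2 arm contrast:
- Equal correlation 0.5: complete case −0.043; MRI-only mixed model −0.044; mixed model with the score 0.000.
- Equal correlation 0.7: −0.043; −0.033; 0.000.

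In a separate run with other assumptions, complete-case bias was 0.00 and the MRI-only model left about −0.03 to −0.04, which returned to 0.00 once the score was included.

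**The case against.** **The benefit can be overstated.** A reader might infer that a mixed model removes missing-at-random bias outright. It does so only if the predictors of loss are in the model and the mean and covariance are correctly specified. Symptoms are a plausible reason for missing a scan in a psychotherapy trial, and an MRI-only model does not contain them. Across the settings examined it left about 0.02-0.06 SD, sometimes more than complete cases. A single covariance for patients and healthy controls with different correlations could leave a further 0.02-0.03 SD. This objection stands and shapes the remedy.

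**The precision gain is modest.** The heading names intervals and the sentence singles out T1-T2, so pairwise fitting is a natural reading; the text does not settle it. Under pairwise fitting, with only T2 missing, T0-T1 gains nothing and the other contrasts gain 3-9% in standard error. The 12-29% figure should not be read as the plan's loss. This stands.

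**The plan may already cover it.** The association paragraph plans a mixed model for change over time. It is labelled as an association analysis, however, and does not replace the ANOVA sentence. The SAP also does not say which test decides whether a measure counts as affected by therapy, so the link from this ANOVA to the later model is a reasonable reading, not a stated rule.

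**Silence is not an error.** A reader might treat the missing-scan rule or the joint-or-pairwise question as a flaw in itself. These are unstated details, and one protocol passage was not available for review. The point rests on the named method.

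**Conclusion.** The point holds as a worthwhile, inexpensive improvement. The named ANOVA uses only participants with every scan in the fit. Under the assumed loss and correlations this costs 3-9% in standard error for T0-T2 and T1-T2 on either reading, and 12-29% for T0-T1 only if fitted jointly. If loss depends on observed MRI values it can also bias change: 0.03-0.18 SD for within-subject T1-T2 at 30% T1-dependent loss. Choosing pairwise fits does not avoid that bias.

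None of these figures is an estimate for this trial. The documents do not support saying that the planned results will be biased, or that a mixed model would be free of bias. What they support is that it would keep partial data and be valid under a weaker and explicit assumption: missing-at-random given the variables included.

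**What to change.** For extracted RSFC, Glx and GABA values, replace the ANOVA with a likelihood linear mixed model (SPSS MIXED) on all available T0, T1 and T2 scans:
- Group, visit and group-by-visit; T0 kept as an outcome with free means in each group, since the supplied text does not state that allocation was randomised.
- Unstructured covariance, allowed to differ between patients and healthy controls if the data support it; Satterthwaite degrees of freedom.
- Between-group T0-T1, T1-T2 and T0-T2 contrasts and within-group T1-T2 change from this model, with the number of scans behind each.
- Recorded clinical scores that predict scan loss brought in as auxiliary variables, in a joint model or in multiple imputation. A post-treatment score should not be a plain covariate, because that would change the effect being estimated.
- A sensitivity analysis shifting one arm's unseen T2 values by 0, ±0.2, ±0.4, ±0.6 and ±0.8 SD, reporting where the conclusion changes. The arm's T2 mean moves by missing share × shift, for example 0.30 × 0.4 = 0.12 SD.

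Record why each scan is missing or rejected. If the ANOVA is kept, state joint or pairwise fitting and the missing-scan rule.

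The cost is SAP wording, syntax and a little more analysis; the model class and software are already in the plan. A three-visit unstructured covariance has 6 parameters, or 12 if estimated separately for patients and controls. With complete data and free T0 means, contrast variance is unchanged. The downside is reliance on missing-at-random: when loss depended on the unseen T2 value, bias was slightly larger than with complete cases (about 0.16 against 0.13 SD), which is why the shift analysis is needed. Whole-brain RSFC maps are outside this change.

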Borderline Personality Disorder and Emotion Regulation

Effects of emotion-focused vs. cognitive schema therapy interventions on emotion regulation deficits in borderline personality disorder - associations between clinical efficacy, brain network function and local glutamate/GABA metabolism

Ethiks approval 04.06.2018, last time edited

Statistical Analysis Plan

Data evaluation and analysis

The SPSS software package (IBM Corp. released 2013, IBM SPSS Statistics for Windows, Version 25.0. Armonk, NY, USA) will be used to perform the following statistical tests to address verification (or falsification) of the previously formulated hypotheses.

Cross-sectional analysis of baseline (T0) MRI-data

Separate for rs-fMRI and ¹H-MRS data: A seed-based correlation analysis will be used to explore the whole-brain RSFC pattern of the regions being central to this study, i.e., the aMCC and DLPFC. Analysis of variance (ANOVA) will be applied to test for RSFC differences between patient groups and controls, as well as for group differences of the local Glx and GABA concentrations and the Glx/GABA balance in the aMCC and DLPFC between patients and controls.

Associations between rs-fMRI and ¹H-MRS data: A linear mixed model analysis will be performed to investigate differences of associations between RSFC in SN and ECN networks and Glx or GABA concentrations at the aMCC and DLPFC between patients and controls.

Follow-up (T0-T1, T1-T2, T0-T2) analysis of treatment effects on primary and secondary outcome criteria

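### The SAP tests ST-EF vs. ST-AC on change in RSFC, Glx and GABA without adjusting for T0; if arms are randomised the test is valid but less precise than the same data allow

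*SAP*

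**What the plan says.** The SAP's follow-up section on MRI target parameters, under the item on separate rs-fMRI and ¹H-MRS analyses, says: "Analysis of variance (ANOVA) for repeated measures will be applied to test for effects of group belonging". The contrasts and outcomes follow: "ST-EF, ST-AC, and healthy subjects; ST-EF vs. ST-AC) on changes of RSFC, Glx and GABA over time". There are thus two comparisons, one of three groups including healthy subjects and one of the two therapy arms. A within-subject test between T1 and T2 is also planned.

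The section heading gives the intervals: "Follow-up (T0-T1, T1-T2, T0-T2) analysis of treatment effects on MRI target parameters (RSFC, Glx, GABA". The SAP does not list the levels of the time factor or name the term to be tested. That T0 is an outcome level, and group-by-time the relevant term, is inferred from these intervals and from the reference to changes over time.

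T0 is not used as a covariate anywhere in the supplied text. The mixed model for RSFC-metabolite associations covers "changes after 9 weeks (and 6 month respectively) of either therapeutic condition (ST-EF, ST-AC", and its second step consists of "applying the same model including the factor treatment group"; no T0 term is named. T0 imaging values are otherwise used under "Cross-sectional analysis of baseline (T0) MRI-data", which compares patients with controls.

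**The concern.** When T0 is an outcome level, a contrast from T0 to a later visit subtracts the whole T0 value, including its measurement noise. A covariate removes only the part of T0 that predicts the later value. Full subtraction over-corrects whenever the correlation between visits is below 1. This has two consequences.

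- **Precision.** The arm difference has a larger standard error than the same scans allow.
- **Chance imbalance.** If one arm starts higher by chance, regression to the mean makes it appear to decline more. The estimate moves against the imbalance.

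This is the only direct comparison of the two arms on the MRI parameters themselves. It may also matter later: the SAP's analysis linking clinical and neurobiological findings admits only MRI measures that therapy significantly affected. Where that judgement rests on this comparison, lost power can keep a true effect out.

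**Working it through.** **Inputs.** The method, contrasts and intervals come from the SAP. The supplied documents give no arm size, alpha, effect size, SD, between-visit correlation (rho) or allocation method, so there is no planned figure to reproduce. Assumed for illustration: two-sided alpha 0.05, 1:1 randomisation, SD 1 at each visit, rho 0.3 to 0.9.

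**Step 1: variance.** For two arms and two visits, the group-by-time F is the square of the change-score t. Per-patient variances are:

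- change score: 2(1 - rho)
- T0-adjusted: 1 - rho²
- ratio: (1 - rho)(1 + rho) / [2(1 - rho)] = (1 + rho)/2

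The equivalent increase in patients is 2/(1 + rho) - 1.

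| rho | change | adjusted | ratio | equivalent extra patients |
|---|---|---|---|---|
| 0.3 | 1.40 | 0.91 | 0.65 | 54% |
| 0.5 | 1.00 | 0.75 | 0.75 | 33% |
| 0.7 | 0.60 | 0.51 | 0.85 | 18% |
| 0.9 | 0.20 | 0.19 | 0.95 | 5% |

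**Step 2: power against the two-visit test.** Assume n = 25 per arm and an effect of 0.7 SD. The noncentrality is 0.7 / (s × √(2/25)), where s is the square root of the variance above. At rho 0.3 this gives 0.7/(1.183 × 0.283) = 2.09 for the change score (48 df). The adjusted analysis gives 0.7/(0.954 × 0.283) = 2.59 before a small-sample covariate correction (47 df).

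| rho | change score | T0-adjusted |
|---|---|---|
| 0.3 | 54% | 71% |
| 0.5 | 68% | 79% |
| 0.7 | 88% | 92% |

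**Step 3: power against a three-level ANOVA.** The SAP may intend T0, T1 and T2 in one model. Simulation used 30 per arm, 0.6 SD at both T1 and T2, equal correlations and 4000 runs:

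| rho | three-level group-by-time F | adjusted, T1 only | adjusted, mean of T1 and T2 |
|---|---|---|---|
| 0.3 | 49% | 66% | 85% |
| 0.5 | 65% | 75% | 89% |
| 0.7 | 87% | 88% | 96% |
| 0.9 | about 100% | about 100% | about 100% |

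Under the Step 2 assumptions (25 per arm, 0.7 SD), F against adjusted T1 is 57% vs 72%, 71% vs 79% and 92% vs 92% at rho 0.3, 0.5 and 0.7. The adjusted mean reaches 98% at rho 0.7.

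Part of the last column's gain comes from averaging two visits. The covariate's own share can be separated. The averaged change has variance (1 + rho)/2 + 1 - 2rho = 1.5(1 - rho). The averaged adjusted value has (1 + rho)/2 - rho² = (1 - rho)(1 + 2rho)/2. The ratio is (1 + 2rho)/3, which is 2.4/3 = 0.80 at rho 0.7, so adjustment still contributes there.

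**Step 4: chance T0 difference.** Given an observed T0 difference D, the expected later difference attributable to it is rho × D. The change score subtracts D in full, which leaves rho × D - D = -(1 - rho) × D. For D = 0.3 SD the shift is -0.21, -0.15, -0.09 and -0.03 SD at rho 0.3, 0.5, 0.7 and 0.9. Simulated slopes were -0.72, -0.49, -0.30 and -0.10 for the change score, and between -0.01 and 0.01 for the adjusted estimate.

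**The case against.** The best defence is that the planned analysis is legitimate. Under randomisation it is unbiased on average and keeps its type I error, so this is a choice between two valid analyses. That stands. A reader might infer that the arm comparison is biased or invalid; the documents do not support that. The shift in Step 4 is conditional on an observed T0 difference, and calling that difference chance presumes random assignment. The supplied text is silent on assignment, but protocol pages were removed, so the silence is not a fault of the plan. Without randomisation, T0 adjustment can itself mislead.

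The size of the loss is also unknown. Arm size, rho, effect and equal SDs are all assumed, and at rho 0.9 the variance saving is only 5%. Against a three-level ANOVA, a single-visit adjusted analysis gains essentially nothing by rho 0.7. Both points stand. They limit how much can be claimed but do not reverse the ordering in Step 1, which holds for every rho below 1.

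Two wider readings are tempting. One is that every contrast is affected; in T1-T2 the T0 value is not subtracted, so that contrast is not. The other is that the arms meet nowhere else in the MRI analyses. The SAP's mixed models also compare them, but on associations between measures.

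**Conclusion.** The point holds as a moderate efficiency concern about the T0-T1 and T0-T2 comparisons of ST-EF with ST-AC. If arms are randomised, the planned test is valid but uses T0 less well than it could. Relative to a change score, the gain is material at low to moderate correlation (variance ratio 0.65 to 0.75 at rho 0.3 to 0.5), modest at 0.7 and negligible near 0.9. If one three-level model is intended, the case at rho of about 0.7 and above rests on analysing T1 and T2 together. The conclusion depends on T0 being an outcome level, which is inferred; on roughly equal SDs across visits; and on assumed values of rho and arm size. The documents cannot show how large the loss is in this trial.

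**What to change.** For ST-EF vs. ST-AC only, model each MRI parameter at T1 and T2 with that parameter's T0 value as covariate. This can be an ANCOVA per visit, or SPSS MIXED with arm, visit, arm-by-visit, T0 and T0-by-visit. Report the adjusted arm difference with its 95% CI, and state which estimate (each visit or the T1/T2 average) is the main one. Use this result wherever the later clinical-neurobiological analysis relies on the arm comparison.

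Keep the unadjusted repeated-measures comparison for healthy subjects, who are not a treatment arm and whose true T0 level may differ. Keep the T1-T2 within-subject test. State how arms are assigned; if not at random, show the change-score result beside the adjusted one.

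The cost is a short SAP revision, a few model degrees of freedom and no new data. If RSFC is analysed as whole-brain maps rather than regional values, the T0 covariate differs by voxel and the imaging software must support that.

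### The follow-up MRI analysis makes 12 to 42 or more tests with no stated significance level, adjustment or lead contrast, although its tests are meant to decide hypotheses

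*SAP*

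**What the plan says.** The opening of the SAP (Data evaluation and analysis) gives the purpose of its tests as "verification (or falsification) of the previously formulated hypotheses". They are therefore not presented as exploratory.

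The follow-up MRI section is headed "Follow-up (T0-T1, T1-T2, T0-T2) analysis of treatment effects on MRI target parameters" and names three parameters: RSFC, Glx and GABA. Its first paragraph, on rs-fMRI and ¹H-MRS data taken separately, plans repeated-measures ANOVA on "changes of RSFC, Glx and GABA over time". The group factor is compared in two ways: "ST-EF, ST-AC, and healthy subjects; ST-EF vs. ST-AC". The same sentence adds tests of change within subjects from T1 to T2.

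The next paragraph of that section, on associations between RSFC and metabolites, supplies the two regions, aMCC and DLPFC. The SAP's paragraph on clinical outcome and neurobiological findings then takes forward the MRI measures on which therapy had a significant effect, again listing all three intervals, and compares the resulting interactions between the two therapies.

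The available documents give no significance level for these tests, no multiplicity adjustment, no order of testing, and no lead parameter, region, interval or comparison. They also do not say whether one ANOVA spans T0, T1 and T2 or a separate one is fitted per interval.

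**The concern.** When many tests can each support a hypothesis and none is named as decisive, a significant result somewhere is weak evidence. Here the tests also overlap. The T0-T2 change is the sum of the T0-T1 and T1-T2 changes, and both group comparisons contain the two therapy arms, so one underlying question gets several chances.

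Two things are at stake. First, a reader of the results could not tell which test settles the question of whether the two therapies differ in their effect on the brain measures. Second, significance is used as a filter: measures that pass enter the model linking brain change to clinical improvement. Any false positive from the first stage becomes an input to the second.

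**Working it through.** The documents state no test count, significance level, sample size or power, so there is no figure of the plan's own to reproduce. The count and the error rate have to be built up.

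**Inputs from the SAP**
- Parameters: 3 (RSFC, Glx, GABA).
- Regions: 2 (aMCC, DLPFC), named in the neighbouring paragraph of the same section and in the baseline analysis.
- Group comparisons: 2 (three groups; ST-EF against ST-AC).
- Intervals: 3 (T0-T1, T1-T2, T0-T2).
- Within-subject T1-T2 tests: 3 × 2 = 6 if patients are pooled; 6 × 3 = 18 if done in each of three groups.

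**Assumptions (not in the documents)**
- Two-sided 0.05 per test.
- One RSFC value per seed region.
- For the simulation: three groups of 20 or 40, no true change or group difference, correlation 0.6 between time points, correlation 0, 0.3 or 0.6 between the six parameter-by-region measures, 3,000 runs per setting.

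**Formulas**
- Expected false positives with k tests: 0.05 × k, whatever the dependence.
- Chance of at least one if independent: 1 − 0.95^k.
- Chance of at least one with the real overlap: simulated. Intervals were tested on change scores; the 12-test reading used the group-by-time F test; the six within-subject tests used pooled patients.

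| Reading | Tests (k) | Expected false positives | At least one, independent | At least one, simulated |
|---|---|---|---|---|
| One ANOVA over T0, T1, T2 | 3 × 2 × 2 = 12 | 0.6 | 46.0% | 28% to 38% |
| Same, plus within-subject T1-T2 | 12 + 6 = 18 | 0.9 | 60.3% | 39% to 54% |
| Each interval tested | 3 × 2 × 2 × 3 = 36 | 1.8 | 84.2% | 53% to 71% |
| Same, plus within-subject T1-T2 | 36 + 6 = 42 | 2.1 | 88.4% | 61% to 78% |

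The independent column is an upper reference only, because the intervals and group comparisons overlap; the simulated column is the one to use. Within each range the lower end comes from the highest correlation between measures. Group size makes little difference.

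With 18 within-subject tests the count would be 36 + 18 = 54. If the whole-brain seed maps described for baseline are reused at follow-up, RSFC is no longer one test per seed and the count rises further.

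**After narrowing.** One contrast and one interval leave 3 × 2 = 6 tests. Unadjusted, the chance of at least one false positive is 1 − 0.95^6 = 26.5% if independent and 19% to 26% in simulation. With Holm the smallest p-value is compared with 0.05/6 = 0.0083, and the simulated rate is about 5% or less, within simulation error.

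**The case against.** The strongest objection is about the count. A repeated-measures ANOVA on change over time ordinarily means one group-by-time test per measure and comparison. That gives 12 tests, for which the chance of a false positive is 28% to 38%, so below one half. This reading is open on the text. Against it, the paragraph on clinical outcome attaches the three intervals to the measures affected by therapy, which suggests that significance is also judged interval by interval. The SAP does not settle the matter.

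A reader might go further and infer that the plan contains exactly 36 tests, that the chance of a false positive is 84%, and that a hypothesis will probably be confirmed by chance. The documents do not support this.
- The figure 36 appears nowhere in them. It holds only if intervals are tested separately, and even then it omits the within-subject tests.
- The 84% assumes independence, which the overlap rules out.
- A significant result somewhere is not the same as confirmation of a particular hypothesis. Half of the 36 are three-group tests that include healthy subjects. The ST-EF against ST-AC tests alone number 3 × 2 × 3 = 18 and give about 40% to 56% in simulation.
- The three-interval heading "Follow-up (T0-T1, T1-T2, T0-T2) analysis of treatment effects on primary and secondary outcome criteria" governs the clinical analysis by reliable change index and adds nothing to the MRI count.

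Finally, the hypotheses that the SAP refers to are not reproduced in the available documents, and part of the protocol file is not available. A lead contrast may be named there. The criticism is therefore limited to what the available text states.

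**Conclusion.** The point holds in this form: between 12 and 42 or more follow-up MRI tests, depending on how the ANOVA is set up, with no stated significance level, adjustment or lead contrast in the available documents. The chance of at least one false positive is roughly 30% to 80%. No reading brings it near 5%, and that conclusion does not depend on the choice between 12, 36 or 42. Whether a false positive is more likely than not does depend on that choice: it is on the 36- and 42-test readings, is not on the 12-test reading, and is borderline with 18.

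The size rests on an assumed 0.05 per test, the assumed group sizes and correlations, and a single RSFC value per seed. This is more than missing detail, because the plan followed as written would let chance findings count towards its hypotheses and pass into the clinical association model.

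**What to change.** Amend the SAP wording as follows.

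1. State the significance level and whether the repeated-measures ANOVA spans all three time points or is fitted per interval.
2. Name one confirmatory MRI contrast and interval, in line with the hypotheses already formulated. ST-EF against ST-AC on the T0-T1 change is the natural candidate: the title sets the two therapies against each other and the programme lasts 9 weeks. The choice is the sponsor's; what matters is that it is fixed in advance.
3. Define one RSFC summary per seed in advance, so that each parameter and region yields one test.
4. Apply Holm across the resulting six tests. A 5% false discovery rate is not a substitute if family-wise error is to be held at 5%, since it controls a different quantity.
5. Report the other intervals, the three-group comparison and the within-subject T1-T2 changes as exploratory estimates with confidence intervals.
6. Describe the model linking MRI measures to clinical outcome as exploratory for any measure selected from uncorrected tests.

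No analysis is lost and no data collection changes. The cost is a stricter threshold for each of the six confirmatory tests, starting at 0.0083 for the smallest p-value. Keeping all 36 tests confirmatory under Bonferroni would cost far more: 0.05/36 = 0.0014 per test, with a simulated family-wise rate of 3.0% to 4.2%.
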